Project Title: Airway Clearance for Pediatric and Adult Cystic Fibrosis Patients Using a Portable Intra-Pulmonary Percussion Device

Investigator(s): [name], [name], [name], [name], [name].

Abstract:

Airway clearance has a crucial role in the prevention of progression of lung disease in cystic fibrosis patients. Despite multiple options available for airway clearance, frequently cystic fibrosis patients have difficulties performing regular airway clearance in an at-home environment. We will compare pulmonary function testing and patient satisfaction with their current home device compared to the portable internal airway percussion device proposed (PIAPD). Our hypothesis is that there is no difference in pulmonary function testing after using PIAPD comparing to their home device. Our goal is to provide an equally effective, less expensive, alternative airway clearance technique for cystic fibrosis patients.

Background:

Cystic Fibrosis (CF) is an autosomal recessive disease that affects more than 30,000 people in the United States and more than 70,000 worldwide. The abnormal Cystic Fibrosis Transmembrane conductance regulator (CFTR) function leads to multiple organ manifestations. In the lungs, the dysfunctional CFTR mutation leads to abnormal thick, sticky mucus in the airways that traps microorganisms, leading to infections, inflammation and respiratory failure, which are the main causes of death in CF patients. Daily airway clearance plays a key role in preventing lung function deterioration in CF. Typically, a CF patient gets airway clearance therapy at least two times daily, each session lasting for about 30 minutes. There are different types of airway clearance therapies. Some of them are active, requiring patient cooperation and some coordination of breathing, while others are predominantly passive. In the United States, the most commonly utilized technique is high frequency chest wall oscillation, more commonly known as “the VEST”. This vibration loosens secretions in the bronchi that the patient will have to actively expel. The apparatus of vest therapy involves a wearable jacket, a hose pipe and an air compressor. This apparatus requires electric supply from the mains and is not portable.

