The PIAP device,(as pictured in Figure 4) that we have developed has been previously tested in several IRB-02 approved pilot studies here at the University of Florida by [name] in a population of healthy volunteers. Published results of these studies report this device's waves produce vibrations within the airways, loosening Airway Surface Liquid (ASL), enhancing airway clearance and decreasing the sense of breathing effort. Furthermore, the IAP device was found to painlessly increase exhalation of intra airway molecules and droplets in healthy individuals.

For this study, we would like to test this unique, custom designed, inexpensive, portable IAP device (PIAPD) as a comfortable alternative for airway clearance in CF patients.

Specific Aims:

1. To determine if Portable Internal Airway Percussion Device (PIAPD) is a non-inferior at-home method of airway clearance in patients with CF, we will compare changes in pulse oximetry and forced expiratory volume in one second (FEV1) prior to and 2 hours after airway clearance performed with standard airway clearance devices vs. the PIAPD. The primary endpoint will be a comparison of results of the aforementioned pulmonary function testing between the two devices.
2. Secondary endpoints include will include comparison of patient satisfaction (tolerability and acceptability) with standard airway clearance devices and PIAPD.
3. We will measure CF patient perception of breathing effort and device use for both methods.

Study Design: This is a pilot study where we aim to compare initial use of the standard airway clearance device (SACD) (as pictured in Figure 2) with subsequent use of a PIAPD in patients ages 6-21 years with stable CF. Our primary hypothesis, stated as Null, is that there is no effect of on FEV1 2 hours after use and there is no effect on perception of effort and efficacy for the PIAPD device.

General Inclusion Criteria:

- Ages 6-21 years
- Stable CF as determined by pulmonary physician assessment
- Assents to forego additional experimental treatments during the study
- Currently using and familiar with airway clearance therapy for treatment of CF
- Participant (or parent or legal guardian if the participant is a minor) is willing to provide Informed Consent

General Exclusion Criteria:

- FEV1 < 40% predictive
- Pneumothorax
- Hemoptysis

- COVID-19 diagnosis within last 14 days
- Non-compliance
- Inability to obtain informed consent

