We shall cross-tabulate the pre- and post-treatment spirometry measures for study condition and group. Significance for association will be obtained by repeated measures ANOVA. The false positive and false negative rates will be estimated by exact binomial confidence limits. This is a pilot study that is seeking a promising outcome as opposed to a definitive one. We shall consider the result as promising if (a) no false positives occur and (b) the false negative rate is below 50%.

Power/Sample Size: The study will have a goal to recruit 50 CF (10 inpatient and 40 outpatient) patients. Initial data analysis to be completed after the first 25 patients have completed each test condition.

Measurable outcomes and expected timeline: We expect the PIAPD is equal to standard airway clearance in CF patients. We expect PIAPD will decrease the sense of breathing effort and increase patient sense of efficacy.

Compliance/Accountability/Regulatory

Statement of Compliance

This study will be conducted in compliance with the protocol and will be generally consistent with current Good Clinical Practices (GCP), adopting the principles of the Declaration of Helsinki and all applicable regulatory requirements (ICH E6, 45CFR46, and FDA 21CFR sections 11, 50, 56, 312).

Prior to study initiation, the protocol and the informed consent documents will be reviewed and approved by UF's Institutional Review Board (IRB). Any amendments to the protocol or consent materials will be approved before they are implemented.

Adverse Event Reporting and Safety Monitoring

In the event of an adverse event the following definitions and processes will be used/followed:

Adverse Event Definitions

In this clinical research study, an adverse event (AE) is any occurrence or worsening of an undesirable or unintended sign, symptom or disease that is associated with study procedures. As an observational study, AEs occurring between study visits will not be reported unless deemed associated with study procedures. Throughout the study, the investigator must record AEs related to study procedures on source documents regardless of severity.

Unexpected Adverse Event

An AE is considered unexpected when the nature (specificity) or severity of the event is not consistent with the risks described in the protocol or informed consent document for specific protocol-required interventions.

Grading Adverse Event Severity

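### The primary null in Study Design is garbled and, as printed, names only the PIAPD, which conflicts with the between-device primary endpoint; the analysis section does not say which contrast is primary

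*Combined protocol and SAP*

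**What the plan says.** Only one sentence in the combined protocol and SAP is labelled as the primary null. It stands under Study Design and opens: "Our primary hypothesis, stated as Null, is that there is no effect of on FEV1 2 hours after use". It continues: "and there is no effect on perception of effort and efficacy for the PIAPD device". The object of the first *of* is missing, and no comparator appears in either half.

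The other statements of purpose compare devices:

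- Abstract: "Our hypothesis is that there is no difference in pulmonary function testing after using PIAPD comparing to their home device".
- Specific Aims, Aim 1, objective: "To determine if Portable Internal Airway Percussion Device (PIAPD) is a non-inferior at-home method of airway clearance in patients with CF".
- Specific Aims, Aim 1, primary endpoint: "The primary endpoint will be a comparison of results of the aforementioned pulmonary function testing between the two devices".
- Measurable outcomes: "We expect the PIAPD is equal to standard airway clearance in CF patients".

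On analysis, the Statistical Analysis section says: "We shall cross-tabulate the pre- and post-treatment spirometry measures for study condition and group". It then assigns significance to a repeated measures ANOVA for association, without saying which term answers the primary question.

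**The concern.** Taken literally, the labelled null says that FEV1 does not change from before to 2 hours after PIAPD use. That is a statement about one device. The primary endpoint, stated a few lines earlier, is about the difference between two devices.

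An ANOVA on pre and post readings by device yields a time term, a device term and a device-by-time term. Only device-by-time addresses the difference in change between devices. An analyst who looks to the labelled hypothesis to choose the term is pointed, on the literal reading, to the pre-to-post change on PIAPD. A retained null could then be taken for the hoped-for absence of a difference when it reflects a device that does nothing. A rejected one could be taken as a favourable result when it says nothing about how PIAPD compares with the standard device.

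**Working it through.** **Step 1. Wording.** The labelled null names one device and no comparator. The abstract hypothesis, the Aim 1 endpoint and the expected result each name or imply two. Aim 1 itself states no null: it is a non-inferiority objective, and the explicit hypothesis of no difference is in the abstract.

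**Step 2. Logic.** Let P and S be the mean 2-hour FEV1 changes on PIAPD and on the standard device. The literal null is P = 0. The between-device null of no difference is P − S = 0.

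- If P = S and both are non-zero, the literal null is false and the no-difference null is true.
- If P = 0 and S is non-zero, the literal null is true and the no-difference null is false.
- If S = 0, the two nulls coincide.

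The conflict therefore has consequences only if the standard device moves FEV1 at 2 hours. The documents do not say by how much it does.

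**Step 3. Illustration.** The recruitment goal of 50 (10 inpatient, 40 outpatient) cannot be reproduced, because no alpha, power, effect size, SD or margin accompanies it. So the following is assumed, not taken from the plan: two-sided 5%; one change score per patient per device; equal SD of change on both devices, set to 1; within-patient correlation ρ of 0 to 0.5; effect d in SD units.

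Both tests are t-tests on n − 1 degrees of freedom, with power from the noncentral t distribution:

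- Within PIAPD: noncentrality = P × √n.
- Device-by-time (paired difference): noncentrality = (P − S) × √n / √(2(1 − ρ)).

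For n = 50 and d = 0.5:

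- Within PIAPD with P = 0.5: 0.5 × 7.07 = 3.54.
- Device-by-time with P = 0, S = 0.5, in absolute value: 3.54 / 1.41 = 2.50 at ρ = 0, and 3.54 / 1 = 3.54 at ρ = 0.5.

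Probability of rejection at n = 50:

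| Assumed truth | Within-PIAPD test | Device-by-time test |
|---|---|---|
| Both devices +0.5 SD | 0.934 | 0.050 |
| PIAPD 0, standard +0.5 SD | 0.050 | 0.688 (ρ = 0) to 0.934 (ρ = 0.5) |
| Both devices +0.2 SD | 0.284 | 0.050 |
| PIAPD 0, standard +0.2 SD | 0.050 | 0.165 to 0.284 |
| Both devices +0.1 SD | 0.107 | 0.050 |
| PIAPD 0, standard +0.1 SD | 0.050 | 0.078 to 0.107 |

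With the 40 outpatients alone and d = 0.5, the within-PIAPD test rejects 0.869 when the devices are equal; device-by-time rejects 0.587 to 0.869 when PIAPD is inert. At the planned first analysis of 25 patients the figures are 0.670 and 0.396 to 0.670.

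The direction follows from the logic. The size depends wholly on the assumed effect of the standard device.

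**The case against.** The strongest reply is that the sentence is visibly broken, so no firm reading should be built on it. If the missing word were *device* or *device type*, the FEV1 half would already be a between-device null. The closing reference to the PIAPD may govern only the perception half. The sentence just before it is comparative ("we aim to compare initial use of the standard airway clearance device (SACD", followed by the PIAPD), as are the abstract, the primary endpoint and the expected result. A sensible analyst would follow the named endpoint. This stands: the within-device reading is the literal one, but it is not certain. It does not remove the problem, because the analysis section names no term that would settle the matter.

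Four stronger readings are tempting, and the documents do not support them.

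- A reader might infer that the trial will test the wrong contrast. No within-PIAPD test is specified anywhere; the contrast is left open.
- A reader might infer that an inert PIAPD would confirm the null, or that an equally good PIAPD would reject it. Failing to reject confirms nothing. Rejection needs both a real 2-hour effect of the standard device and adequate power, and the documents give neither.
- A reader might set 93% against 5% and call it an inflated type I error. The two figures belong to tests of different hypotheses, and the 93% is power against a literal null that is false in that scenario.
- A reader might infer that the trial would declare a wrong result. The only stated success rule concerns false-positive and false-negative rates and is tied to neither FEV1 null.

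The illustration also simplifies the data: outpatients are tested on day 1 and then twice weekly in each two-week period, so they contribute more than one change per device. The study is a pilot, which lowers the stakes, although the plan still calls for a significance test.

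**Conclusion.** The concern holds as a conflict in a stated primary hypothesis. The labelled null is garbled, lacks a comparator as printed, and does not match the between-device endpoint of Aim 1; the analysis section leaves the primary contrast unnamed. It is more than an omission, because two statements of the primary question disagree. It falls short of showing that the trial will run the wrong test.

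If the standard device has a 2-hour effect near 0.5 SD, the choice of contrast reverses which scenario tends to be rejected. If that effect is 0.1 to 0.2 SD, neither test separates the scenarios well at 50 patients. If it is zero, the two nulls coincide. All three effect sizes are assumptions. The plan should be corrected, and the correction does not depend on which effect size is right.

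**What to change.** In Study Design, replace the labelled null with a between-device statement on the FEV1 change from before to 2 hours after airway clearance, in the form that serves Aim 1: the null is that PIAPD is worse than the standard device by at least a pre-stated, justified margin. Restoring only the abstract's hypothesis of no difference would not be enough, because failing to reject it does not show non-inferiority.

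In Statistical Analysis, name the within-patient PIAPD-minus-standard change (the device-by-time contrast), with its confidence interval judged against that margin, as the primary analysis. Report within-device pre-to-post changes as descriptive.

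State the perception hypothesis separately and also between devices. The Measurable outcomes paragraph expects an improvement there, and equality on the FEV1 question, so one joint null serves neither.

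The cost is protocol wording and the choice and justification of a margin; this point asks for no new patients, visits or data. The downside is that a pre-to-post change on PIAPD alone can no longer serve as the primary result. The margin-based test may also have limited power: with an assumed margin of half a 0.5 SD standard-device effect, ρ = 0.5 and a one-sided 2.5% test, 50 patients would show non-inferiority about 41% of the time if the devices were equal.

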- Any condition that, in the opinion of the investigator, would interfere with the study conduct or the safety of the participant

Additional Exclusion Criteria: Outpatient Arm (in addition to general exclusion criteria above)

- Decrease in FEV1 > 10% from baseline over last 12 months
- Antibiotic Initiation for acute CF exacerbation
- Hospitalization for CF Exacerbation

Additional Exclusion Criteria: Inpatient Arm (in addition to general exclusion criteria above)

- Failure to increase FEV1 $\geq 10\%$ from initial PFTs on admission by day 9 of hospitalization.

Our patients will be recruited from our CF outpatient Clinic and from our CF inpatient population. Participants will be randomly assigned to perform airway clearance with the Standard Airway Clearance device (SACD) or Portable Internal Airway Percussion device (PIAPD). A large majority of our patients will be using VEST therapy as their standard of care airway clearance. A few might be using an Intrapulmonary Percussion Device that uses a mechanism different from the device we will be testing. Based on past experience, it is unlikely that this will present a significant source of variability.

After discussing the study with a prospective participant and obtaining informed consent, participants will be randomized to either the standard of care or experimental group:

Outpatient arm:

On day 1, baseline FEV1 as measured on Smart One® portable home spirometer (Figure 1) and pulse oximetry will be obtained before and 2 hours after airway clearance, either performed with SACD method, PIAPD at 15hz. The frequency of the device will stay at 15 hz for the duration of the study as it has been previously shown to be the most effective frequency for better airway clearance (i.e., getting deeper into the airways). Participants will also be asked to give a rating of breathing effort using a Modified Borg Dyspnea Scale.

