For the next two weeks, airway clearance therapy, either performed with SACD method or PIAPD, will be performed by the patient daily (CF patients perform airway clearance daily as part of standard of care for their disease). Spirometry/pulmonary function testing will be collected twice per week over the two-week period with a pre and post FEV1, pulse oximetry, and rating of breathing effort. This testing will be done via telemedicine so that the PI or co-investigator can assist the patient with the PIAPD if necessary and conduct the testing in a safe and efficacious manner. At the end of the two weeks, the participant will be asked to complete a short survey regarding the ease of use and acceptability of the airway clearance device they had been using for the first part of the study.

At the end of the initial 2-week period, the patient will be crossed-over to the other arm of the study and the same procedures will be repeated as per the above procedures. At the end of the study, patients will return the PIAPD device to the study team.

FIGURE 1

Figure 1: Smart One® portable home spirometer is the standard of care for at-home measurement of FEV-1.

Inpatient arm:

Patients who are admitted to the hospital for a normal seasonal disturbance of their CF are admitted, as SOC, for a 14-day in-patient stay. When patients are admitted, they bring their VEST system, as this is the standard of care device used by over 95% of CF patients for airway clearance therapy. Following admission, patients will be informed of the study by the PI or one of the designated co-investigators. All study procedures will be explained and ample time to ask questions will be allotted. If the patient agrees to participate written informed consent will be obtained and the following procedures performed:

Hospital Stay Days 1-3: Patients will only use their SOC airway clearance therapy. This will allow for a “wash-out period” providing all the patients with good airway clearance prior to collecting data (some patients may have had poor compliance prior to hospitalization). The participant will also be asked to complete a short survey regarding the ease of use and acceptability of their SOC airway clearance device, at the end of this 3-day wash-out period. Furthermore, during this period, we will get daily spirometry with a portable spirometer once per day after first airway clearance of the day, along with pulse oximetry.

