Hospital Stay Day 4: If, in the judgement of the PI, the participant has stabilized, we will randomize them to use either their SOC device or the study device. On Day 4, patients will be randomized to SOC or the new airway clearance device. We will collect the patient’s ratings of breathlessness with the Modified Borg Dyspnea Scale and perform spirometry again with the Smart One® portable spirometry device before and two hours after airway clearance procedures for the first airway clearance of the day. We will also obtain pulse oximetry.

Hospital Stay Day 5: we will alternate the modality for the first airway clearance session of the day (using whichever device they were not randomized to use on Day 4), repeating the Modified Borg Dyspnea Scale and performing spirometry again before and two hours after airway clearance along with pulse oximetry. At this point, they will have used both the airway clearance devices, and they will be asked to complete a short survey regarding the ease of use and acceptability of the study airway clearance device.

Hospital Stay Days 6-9: we will continue with daily spirometry, dyspnea measurements and pulse oximetry once per day after the first airway clearance of the day using the study device.

Hospital Stay Days 10-14: patients who have increased their FEV1 by at least 10% from admission by day 9 of hospitalization and whose symptoms have clinically improved, will be given the choice of whether to use their SOC device or the experimental study device. Whichever device they choose, they will use for two airway clearance sessions, along with dyspnea measurements, and pulse oximetry on days 10-14 of hospitalization.

At the end of the two weeks, the participant will be asked to complete a short survey regarding the ease of use and acceptability of each airway clearance device they had been using for the study. At the end of the study, we will ask that the patient return the experimental device to the study team.

FIGURE 2

Figure 2: The Vest® Airway Clearance System is the standard of care for airway clearance in both adult and pediatric

Safety Endpoints:

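### The inpatient exclusion for missing a 10% FEV1 gain by Day 9 can be triggered only after randomisation and the paired device comparison, and conflicts with the Days 10-14 procedures

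*Combined protocol and SAP*

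**What the plan says.** Under Additional Exclusion Criteria: Inpatient Arm, the only added criterion is failure to raise FEV1 by at least 10% "from initial PFTs on admission by day 9 of hospitalization".

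The Inpatient arm section sets the order of events. Consent follows admission. On Days 1-3, "Patients will only use their SOC airway clearance therapy", with daily spirometry. Randomisation is conditional: "If, in the judgement of the PI, the participant has stabilized". It takes place on a fixed day: "On Day 4, patients will be randomized to SOC or the new airway clearance device". Day 5 uses the other device ("using whichever device they were not randomized to use on Day 4"). Both days have measurements before and two hours after the first session. These supply the inpatient part of the primary endpoint in Specific Aims, which compares results "prior to and 2 hours after airway clearance performed with standard airway clearance devices vs. the PIAPD". On Days 6-9 the first session of each day uses the study device, with one spirometry reading after it.

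For Days 10-14, the same section gives a choice of device to patients who have met the FEV1 threshold by Day 9 and whose symptoms have also improved. It does not say what happens to the others. The inpatient paragraph of Safety Endpoints does not list the threshold among the reasons to cease the device. Statistical Analysis names a repeated measures ANOVA and defines no analysis set. Power/Sample Size plans 10 inpatients and 40 outpatients.

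**The concern.** An exclusion criterion normally settles who enters before anyone is randomised. Failure of this one becomes known five days after randomisation and four days after the paired comparison is complete. It rests on FEV1, the variable of the primary endpoint, measured after study-device use. Applied as written, it would select patients on a post-randomisation outcome.

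The two uses of the threshold also differ. A patient with a 10% gain but no symptom improvement is not excluded by the eligibility section, yet is not offered the choice in the procedures. A patient who misses the gain is excluded by one section and not mentioned in the other. Two analysts following the text could build different inpatient datasets.

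At stake are complete Day 4/5 pairs, Days 6-9 data and end-of-stay surveys in an arm of about 10. Satisfaction is less exposed. The standard device is rated early ("acceptability of their SOC airway clearance device, at the end of this 3-day wash-out period"), and on Day 5 "they will be asked to complete a short survey regarding the ease of use and acceptability of the study airway clearance device". Those ratings are lost only if all of a patient's data are dropped.

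**Working it through.** **Timing.** Randomisation is on Day 4, both devices have been used by Day 5, and the criterion is settled at the latest on Day 9. First sessions by Day 9: standard device 3 + 1 = 4 (Days 1-3 and one of Days 4/5); study device 1 + 4 = 5 (the other of Days 4/5, and Days 6-9). The Day-9 gain therefore accrues over both devices, and Days 6-9 have no concurrent standard-device comparison.

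**Plan's own figure.** The goal of 50 cannot be reproduced, because no power, effect size, SD or margin is given. No stated figure is contradicted.

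**Assumptions.** The documents give no Day-9 failure rate and no correlation. I take a retained share p of 0.5 to 0.9 and a correlation ρ of 0.3 to 0.5 between the Day-9 gain and the within-patient device difference. Results are in units of the SD of that difference.

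**Would the case arise?** With failure rate f, P(at least one of 10 fails) = 1 − (1 − f)^10. This is 0.65 at f = 0.1, 0.89 at 0.2 and 0.97 at 0.3.

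**Precision, if those who fail are dropped.** SE = 1/√n. With all 10 it is 0.316. With 9, 7 and 5 left it is 0.333, 0.378 and 0.447, which is 5% to 41% larger. The stability condition on Day 4 may leave fewer than 10 randomised: with 8 randomised and 4 retained, the SE goes from 0.354 to 0.500.

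**Bias, if those who fail are dropped.** With bivariate normal selection from below, bias = ρ·φ(z)/p, where z is the (1 − p) normal quantile. Pooled bias at equal weight and equal SD = bias × 10p/(40 + 10p).

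| p | φ(z)/p | Inpatient bias, ρ = 0.3 / 0.5 | Bias ÷ SE, ρ = 0.3 / 0.5 | Pooled bias, ρ = 0.3 / 0.5 |
|---|---|---|---|---|
| 0.9 | 0.195 | 0.058 / 0.097 | 0.18 / 0.29 | 0.011 / 0.018 |
| 0.7 | 0.497 | 0.149 / 0.248 | 0.39 / 0.66 | 0.022 / 0.037 |
| 0.5 | 0.798 | 0.239 / 0.399 | 0.54 / 0.89 | 0.027 / 0.044 |

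Bias is zero at ρ = 0 and changes sign if ρ is negative. SE = 1/√n ignores the fall in variance that selection causes. At ρ = 0.5 and p = 0.5 the retained SD is √(1 − 0.25 × 0.798²) = 0.917, so the SE is 0.917/√5 = 0.41 and bias/SE is 0.399/0.41 = 0.97, not 0.89.

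**Pooled result.** The pooled SE is 1/√50 = 0.141 to 1/√45 = 0.149, so bias is at most 0.044/0.149 = 0.30 of it. The lowest coverage of a 95% interval is then 93.98%. If the inpatient SD were twice the outpatient SD, pooled bias would be 0.02-0.09 outpatient SD at equal weight, or 0.01-0.02 with inverse-variance weights.

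**The case against.** The strongest reply is that the criterion is a misfiled continuation rule. The procedures repeat the same threshold, baseline and day as the gate to Days 10-14, and that intent is plausible. This stands as a reading, but it does not settle the text: the eligibility section calls it an exclusion, and the two versions differ on symptoms.

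A reader might infer that the plan orders data from these patients to be discarded. It does not. The precision and bias figures describe a literal application, and the plan never says that it will take that step.

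A reader might also infer that the criterion can never be known before randomisation. That goes too far. With daily spirometry on Days 1-3, a patient may meet the threshold before Day 4; only failure has to wait.

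Nor is it right that the 25-patient trigger for the initial analysis is left open by this rule. Power/Sample Size counts patients who have completed each test condition, and the Day 5 text says that both devices have then been used. A patient who later misses the threshold qualifies on a plain reading.

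Finally, this is a pilot, the pooled effect is small, and no stand-alone inpatient estimate is clearly planned. That limits the weight of the point. It does not remove the contradiction about who is analysed.

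**Conclusion.** The point holds as an internal contradiction with an unstated consequence, and it should be fixed. Failure of an inpatient exclusion criterion can be established only after randomisation, the paired comparison and further study-device use. The procedures use the same threshold for a different purpose, and neither Safety Endpoints nor Statistical Analysis resolves the conflict.

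The surest cost of a literal application is precision in the inpatient arm, of the size shown above for an assumed 50-90% retained. Bias is conditional on a correlation that the documents do not give. A reader might infer that the rule favours the study device. The documents do not support that, because the gain accrues over both devices and the sign of the correlation is unknown. Under the assumed values and equal SDs, the pooled effect is about 0.01-0.04 SD with coverage about 94%. The timing conflict itself depends on none of these assumptions.

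**What to change.** Reconcile Additional Exclusion Criteria: Inpatient Arm with Hospital Stay Days 10-14, including the symptom condition, on whether the Day-9 threshold ends participation or only governs entry to Days 10-14. The procedures should also state how patients who miss it are handled. This review takes no position on which clinical rule is right.

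Whichever is chosen, add to Statistical Analysis:

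> No inpatient randomised on Day 4 is removed from the analysis because of the Day-9 FEV1 result. All Day 4 and Day 5 data collected are analysed; patients with only one of the two sessions are reported and contribute the data they have where the model allows. An inpatient who has completed both the Day 4 and Day 5 sessions counts toward the 25 for the initial analysis, whatever the Day-9 result. The number not meeting the Day-9 condition is reported. Days 10-14 device choice and end-of-stay survey results are shown with the number offered the choice or completing the survey beside the number randomised.

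Data from participants who withdraw are handled under the consent terms. The wording should be settled before inpatient results are seen, so that the exclusion is not decided with the outcome known.

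The cost is wording in the eligibility, inpatient procedures and statistical sections, with the usual IRB approval of an amendment. No new data are needed, because the Day 4/5 measurements and the Day 3 and Day 5 surveys are collected before Day 9.

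### The inpatient randomisation time is stated two ways, and no allocation method or split by setting is given: align the text and use separate blocked device-order lists

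*Combined protocol and SAP*

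**What the plan says.** Two parts of the protocol place randomisation.

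- **General recruitment text** (after the inpatient exclusion criteria, before the Outpatient arm heading). It covers clinic and hospital patients together: "Participants will be randomly assigned to perform airway clearance with the Standard Airway Clearance device (SACD) or Portable Internal Airway Percussion device (PIAPD"). It then says that after "obtaining informed consent, participants will be randomized to either the standard of care or experimental group". No condition and no day are given.
- **Inpatient arm.** Consent follows admission: "If the patient agrees to participate written informed consent will be obtained and the following procedures performed". For Days 1-3, "Patients will only use their SOC airway clearance therapy". The Day 4 entry is conditional: "If, in the judgement of the PI, the participant has stabilized, we will randomize them to use either their SOC device or the study device". The next sentence drops the condition: "On Day 4, patients will be randomized to SOC or the new airway clearance device". On Day 5 the patient uses the other device.

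Both settings are crossovers, so the allocation fixes device order: two periods of two weeks for outpatients, two single sessions on consecutive days for inpatients. The Power/Sample Size paragraph sets a goal of "50 CF (10 inpatient and 40 outpatient) patients". The protocol states no ratio, list, block, stratum or concealment. The Statistical Analysis section names a repeated measures ANOVA without period or sequence terms.

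**The concern.** A consented inpatient who has not stabilised by Day 4 is randomised if the general text is followed literally, and is not randomised under the conditional Day 4 sentence. The protocol does not say how that patient is handled or counted.

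Timing matters because stability is a judgement by the PI, the two devices are visibly different, and neither blinding nor concealment is described. An allocation made at consent could be known when stability is judged and could influence who proceeds. Patients who did not proceed would be losses after randomisation.

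The second issue is balance. With only 10 inpatients and no restriction on the randomisation, device order can come out uneven by chance. Inpatients are expected to be recovering, since the schedule looks for an FEV1 gain of at least 10% from admission by Day 9. A difference between Day 4 and Day 5 that owes nothing to the device is therefore plausible, and no period term is planned to remove it.

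**Working it through.** **Plan's own figure.** 10 + 40 = 50, which agrees. The protocol gives no effect size, SD, margin or power, so 50 cannot be derived further.

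**Assumption.** Simple 1:1 randomisation, since no ratio or method is stated.

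**Order split among 10 inpatients**, X ~ Binomial(10, 0.5):
- 3:7 or worse: 2 × (1 + 10 + 45 + 120)/1024 = 352/1024 = 34.4%.
- 2:8 or worse: 2 × (1 + 10 + 45)/1024 = 112/1024 = 10.9%.
- If instead one list were balanced 25:25 over all 50 without regard to setting, the hypergeometric probabilities are 28.9% and 7.4%.

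**Effect on the inpatient contrast.** Let a patients take the standard device first and b = 10 − a take the PIAPD first. Let δ be the device difference in within-session change, and π the Day 5 minus Day 4 shift in that change. A patient's PIAPD-minus-standard difference has expectation δ + π in the first order and δ − π in the second. The unadjusted mean is therefore δ + π(a − b)/10. Adjusting for period removes π but multiplies the variance by 25/(ab) relative to 5:5.

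| Split | Share of π carried, unadjusted | Variance inflation, adjusted | Efficiency, ab/25 |
|---|---|---|---|
| 5:5 | 0 | 1.00 | 100% |
| 4:6 | 20% | 25/24 = 1.04 | 96% |
| 3:7 | 40% | 25/21 = 1.19 | 84% |
| 2:8 | 60% | 25/16 = 1.56 | 64% |

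**If inpatients were allocated at consent.** The protocol gives no rate of failing to stabilise by Day 4. Assuming 10%, 20% or 30%, expected losses are 1, 2 or 3 of 10. The chance of at least one is 1 − 0.9^10 = 65%, 1 − 0.8^10 = 89% or 1 − 0.7^10 = 97%.

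**After the change.** With an inpatient list in blocks of 4 (illustrative), two full blocks give 4:4. The first two places of the third block give 5:5 overall with probability 4/6, and 6:4 or 4:6 with probability 2/6. Variance inflation is then at most 1.04. No inpatient is lost between allocation and the stability check.

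**The case against.** The general text does not say that randomisation is immediate. Day 4 is also after consent, every inpatient uses the standard device until then, and a specific schedule normally governs a general lead-in. On that reading, patients who do not stabilise leave before allocation, and no allocation exists to influence the decision. This stands. A reader might infer that the plan loses inpatients after randomisation at the stability check, but that needs the general text to mean allocation at consent, which it does not say.

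A reader might also infer that inpatient order will be badly unbalanced. It need not be: even under simple randomisation, 66% of allocations are 4:6 or better, and every patient uses both devices.

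Nor does general recovery between Day 4 and Day 5 bias the comparison by itself. Specific Aims defines the endpoint as the change from before to 2 hours after a session, so a higher FEV1 level on Day 5 largely cancels. Bias needs a shift in the within-session response, or carry-over. The 40% and 60% are shares of an unknown quantity in an inpatient-only contrast, and the protocol does not clearly specify such a contrast. If all 50 patients were pooled with equal weight (an assumption), the inpatient contribution at 3:7 would be 0.4 × 10/50 = 8% of the shift.

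Finally, this is a pilot that does not claim to be definitive. That limits the consequence, but it does not justify leaving the randomisation time and method open when stating them costs almost nothing.

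**Conclusion.** The texts differ and should be aligned. The inpatient schedule probably governs, so this is an ambiguity with avoidable risks, not evidence that the trial will lose randomised patients. If staff did allocate at consent, at least one loss among 10 would be likely under the assumed rates of 10% to 30%.

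The firmer gap is that no method, restriction or stratification is stated for a stratum of 10. Under assumed simple 1:1 randomisation, the chance of 3:7 or worse is 34% and of 2:8 or worse 11%. The cost is 40% or 60% of any shift in within-session response if period is ignored, or efficiency of 84% or 64% if it is adjusted for. The documents do not give the size of that shift. The change is a cheap improvement worth making before enrolment.

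**What to change.** 1. Amend the general recruitment text to state one time point per setting: outpatients are randomised after consent, and inpatients on Day 4 after the stability decision has been recorded. Make the two Day 4 sentences agree.
2. Use two concealed blocked lists, one per setting, with undisclosed block sizes, aiming at about 20:20 and 5:5.
3. Describe the allocation as device order, not as membership of a standard or experimental group. Reconcile this with the Study Design paragraph, which describes the standard device first and the PIAPD afterwards.
4. Report inpatients who consent but do not stabilise as not randomised, and say whether the goal of 10 counts consented or randomised patients.
5. Include period and sequence in the repeated measures model in the Statistical Analysis section.

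The cost is protocol wording and two lists prepared in advance, with no extra visits. The drawback is slight predictability near the end of blocks, since the devices are not blinded. Very small fixed blocks would make it worse: with blocks of 2, every second allocation could be predicted.
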